- *Informed Consent and Onsite Screening Visit:* Volunteers who pass the phone screen will be invited to participate in on-site screening. Informed consent will be obtained. Mobility function, cognitive screening, and somatosensory screening will be conducted. This visit will last approximately 3 hours.
- *Study Intervention Visit(s):* Qualifying participants will be invited to participate in the full study. They will attend either one or two intervention sessions (randomly determined to study dosage effects) in which they will practice a “locomotor learning” task comprised of a 10m walking course with obstacles and transitions between hard and soft floor surfaces. During this task they will receive either active or sham transcutaneous spinal direct current stimulation. They will also wear either smooth or textured shoe insoles. Biomechanical and neural control of walking will be assessed with various non-invasive

modalities. Participants will also undergo H-reflex assessment. This visit will last approximately 3 hours.

- *Follow up Visit:* 2 days following the study intervention visit, participants will return to perform the “locomotor learning” task again so that we can assess retention of learning. This visit will last approximately 2 hours.

Telephone Screening

Participants will be screened by telephone to determine if they meet the following criteria:

Inclusion criteria

- Age 65 years or older
- Willingness to be randomized to either intervention and to participate in all aspects of study assessment and intervention

Exclusion criteria

- Diagnosed neurological disorder or injury of the central nervous system, or observation of symptoms consistent with such a condition (spinal cord injury, Alzheimer’s, Parkinson’s, stroke, etc.)
- Contraindications to non-invasive spinal stimulation including any prior spinal surgical procedure
- Chronic lower back pain
- Obesity, defined as Body Mass Index exceeding 30. This is due to the potential influence of body fat on the amplitude of electrical current flow to the spinal cord.
- Use of medications affecting the central nervous system including, but not limited to, benzodiazepines, anti-cholinergic medication and GABAergic medication.
- severe arthritis, such as awaiting joint replacement
- current cardiovascular, lung or renal disease; diabetes; terminal illness
- myocardial infarction or major heart surgery in the previous year

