Health monitoring and medical response: Volunteers at risk of health problems due to recent history of medical conditions (e.g., serious cardiac or pulmonary conditions) will be excluded, as noted above in the inclusion/exclusion criteria. Any adverse events will be recorded and monitored as required by our University of Florida Institutional Review Board. In the event of a medical emergency at the VA Hospital (our study site) we will call the hospital emergency response line, [name] and alter them to a code blue (medical emergency). Subjects will be able to terminate a study session at their request at any time without prejudice. Minimization of risk during neurorehabilitation and assessments will be accomplished by monitoring vital signs, with prescribed criteria for termination of the testing session. Vital signs will be monitored before, during and after assessment. Contraindications for participation will include resting heart rate >100 bpm or <50 bpm, resting systolic blood pressure >180 mmHg or <100 mm Hg or resting diastolic blood pressure >100 mmHg. Indications to terminate physical activity will include heart

rate that exceeds age-predicted maximum (220-age), sudden drop in heart rate exceeding 15 bpm, systolic blood pressure >220 mmHg or <100 mmHg, or diastolic blood pressure >110 mmHg. Other criteria for termination include subject complaints of shortness of breath, light-headedness, dizziness, confusion, severe headache, dyspnea or onset of angina. Should the session be halted, the subject will be asked to rest while BP and HR are monitored and will resume only if BP and HR return to acceptable values. If any of these conditions persist after rest, the patient's primary physician will be called and patient referred for evaluation. If the patient complains of angina at rest, loss of consciousness occurs, or cardiac arrest, emergency medical services through 911 will be called immediately. Portable defibrillators are available.

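### Angina or confusion that halts a session and clears with rest needs only acceptable blood pressure and heart rate before walking resumes, with no medical evaluation required

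*Combined protocol and SAP*

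**What the plan says.** The rule is in the paragraph on health monitoring and medical response, under Protection Against Risk. It has four parts.

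- **Vital-sign limits during activity.** Activity stops for a heart "rate that exceeds age-predicted maximum (220-age), sudden drop in heart rate exceeding 15 bpm", or for blood pressure outside stated limits (systolic above 220 or below 100 mmHg, diastolic above 110 mmHg).
- **Symptom limits, listed separately.** "Other criteria for termination include subject complaints of shortness of breath, light-headedness, dizziness, confusion, severe headache, dyspnea or onset of angina".
- **After a halt.** The participant rests with blood pressure and heart rate monitored and "will resume only if BP and HR return to acceptable values".
- **Escalation.** "If any of these conditions persist after rest", the participant's "primary physician will be called and patient referred for evaluation". A separate sentence deals with emergencies: "If the patient complains of angina at rest, loss of consciousness occurs, or cardiac arrest, emergency medical services through 911 will be called immediately".

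The Telephone Screening exclusions include "current cardiovascular, lung or renal disease; diabetes; terminal illness". They also include a diagnosed central nervous system disorder or injury, "or observation of symptoms consistent with such a condition".

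**The concern.** The condition for resuming does not match the reason for stopping. Where a symptom caused the halt, blood pressure and heart rate may never have been out of range, so acceptable readings say little about whether the participant is safe to continue. Both escalation steps miss an episode that comes on with effort and settles with rest.

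Participants are 65 or older and are told to walk the obstacle course at the highest speed they can safely manage. The protocol states that they gain no direct benefit. New exertional angina suggests possible cardiovascular disease, and transient confusion a possible central nervous system disorder. Both are grounds for exclusion, so an in-session episode may be the first sign that screening missed an ineligible participant. The listed onsite screening measures include no cardiac test beyond resting blood pressure, and review of medical records is optional. Under the written rule, that person could go on walking the same day and return for later visits with no required medical evaluation and no required re-check of eligibility.

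**Working it through.** There is no planned figure to reproduce. The check is to follow the rule through each case and then count the walking exposure that it leaves open.

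**1. Cases after a symptom-triggered halt (health monitoring paragraph)**

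| Course of the symptom | Action the text requires |
|---|---|
| Angina at rest, loss of consciousness or cardiac arrest | 911 call |
| Symptom persists after rest | Physician call and referral |
| Symptom clears with rest, blood pressure and heart rate acceptable | None; resuming is permitted |

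The third row is the gap. Seven complaints are listed: shortness of breath, light-headedness, dizziness, confusion, severe headache, dyspnea and onset of angina. The concern is with 2 of them, confusion and angina, because these bear most directly on the cardiovascular and central nervous system exclusions.

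**2. Can a symptom be the only trigger?**

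The heart-rate limit is 220 − age: 155 bpm at age 65, 145 at 75 and 135 at 85. Take assumed values for illustration: a 75-year-old with angina at 120 bpm and 170/90 mmHg.

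- 120 < 145 bpm, 170 < 220 mmHg and 90 < 110 mmHg. No activity limit is crossed, so the halt rests on the symptom alone.
- The protocol does not define acceptable values for resuming. Against the activity limits, this participant already meets them. Against the resting limits in the same paragraph (heart rate 50 to 100 bpm, systolic 100 to 180 mmHg, diastolic up to 100 mmHg), only heart rate has to fall, from 120 to 100 bpm or below.

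On either reading, the test can be met without anyone assessing the angina.

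**3. Walking still open to one affected participant**

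The walking practice protocol sets N = 10 to 20 passes of 10 m, with about one minute of rest between passes. After a halt at pass k, N − k passes remain.

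| Halt at | N = 10 | N = 20 |
|---|---|---|
| First pass | 10 − 1 = 9 | 20 − 1 = 19 |
| Mid-session | 10 − 5 = 5 (50 m) | 20 − 10 = 10 (100 m) |
| Last pass | 0 | 0 |

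Up to 20 of the 40 participants repeat the practice session. One of them halted in the first session has 10 to 20 further passes to come. All participants then have several more walking trials at the follow-up visit, about two days after the intervention visit.

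These counts show possible exposure. They are not estimates of risk or harm.

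**4. Does another section close the gap?**

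| Provision | Why it does not |
|---|---|
| Vital signs checked before, during and after assessment; resting limits for participation | Vital signs only; no question about a prior symptom |
| Principal Investigator may declare a person ineligible (onsite screening section) | Permissive; no evaluation required |
| Clinical judgment of the team (telephone screening) | An entry criterion; no evaluation after an event |
| Adverse-event recording and reporting | Reporting only: 5 working days if serious and unexpected, otherwise annually |
| Questionnaires and follow-up call (risks section) | Directed at reactions to the stimulation |
| Code-blue line, defibrillators, gait belt, attending staff | Emergency response and fall protection |

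None requires a medical evaluation or clearance after a resolved episode.

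**The case against.** The strongest reply is that the gap is narrow and already surrounded by safeguards. The symptoms are called criteria for termination. The resumption sentence sets a necessary condition and obliges nobody to restart. A symptom that persists leads to referral, and angina still felt during the enforced rest could reasonably be read as angina at rest, which brings a 911 call. The site is a hospital, vital signs are taken before each assessment, and the Principal Investigator's power to stop further participation is not limited by its wording to the screening stage. The exclusions make such events unlikely, and competent staff might well stop anyway.

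Much of this stands. It confines the problem to episodes that clear once walking stops, and it lowers the chance of harm. It does not supply the missing step: the sentence after the termination criteria expressly allows the session to resume, and every other safeguard is discretionary, limited to vital signs, specific to the stimulation, or a matter of emergency response or reporting. Even reporting within 5 working days could come after the two-day visit.

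Two further objections have some force. The protocol does not rank the seven complaints, so singling out angina and confusion is a clinical judgment. It rests on their link to the exclusions, but the team could reasonably add others, such as severe headache. A lighter remedy, requiring the symptom to resolve and a clinician to document a review before restarting, would deal with most of the same-day problem. It would not by itself require eligibility to be re-checked before later visits.

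**Conclusion.** The concern holds. Followed exactly, the written rule lets a participant whose exertional angina or confusion has cleared with rest go back to fast obstacle walking on the strength of blood pressure and heart rate alone. No evaluation is required that day, before a second session or before the follow-up visit.

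The number affected is unknown, because the documents give no event rate, and it is probably small given the exclusions. The case for a change rests on how serious one such event could be, and not on its likelihood. The conclusion assumes that the symptom has fully cleared with rest and that staff apply the text as written, without using discretion to stop. It is a participant-safety point that should be corrected; it does not affect the validity of the planned effect-size estimates.

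**What to change.** Add to the health monitoring paragraph, in words such as these:

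> Onset of angina or confusion during activity ends that day's session, even if it resolves with rest. The participant's primary physician is contacted, the participant is referred for medical assessment, and eligibility is re-checked before any further practice session or the follow-up visit. Confusion here means disorientation, not errors on the serial-7 or verbal fluency tasks.

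For the other five complaints, state that the symptom must have resolved, in addition to blood pressure and heart rate being acceptable. The sentence on persisting conditions already implies this. It would also help to say which limits count as acceptable for resuming.

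The change is a few sentences and extends a referral route that the paragraph already contains. A few sessions would end early, and a participant awaiting assessment might miss the two-day retention test. Each such loss is 1/40 = 2.5% of participants, or 1 of 10 in a group if the four groups are equal (40/4 = 10). That is tolerable in a study whose Statistical Analysis Plan disclaims power for tests of group differences.

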reflex^{21,22}, increases corticospinal excitability²⁴, and increases motor unit recruitment.⁴¹ We propose to deliver tsDCS using an electrode montage that targets lumbar spinal excitability, and has been validated by modeling of electrical current flow⁴² and by gains in lower extremity motor performance.²⁵ The objective with tsDCS is to bring spinal neurons closer to their discharge threshold. When applied during walking, this increased excitability of spinal neurons contributes to a physiological environment that is more responsive to task-specific activation by descending/motor and afferent/sensory pathways.²² The proposed study is designed to provide evidence of short term effects of tsDCS on task practice, which can be translated to longer rehabilitation interventions in the future.

5. Specific Aims:

Specific Aim 1: Acquire preliminary data to assess whether active tsDCS and/or textured shoe insoles improve practice-related gains in performance and retention for a complex obstacle walking task.

Hypothesis 1a: Within-session, effect sizes will support the following group differences for improved walking speed and reduced prefrontal activity after the practice period:
[active/textured] > [active/smooth = sham/textured] > [sham/smooth]

Hypothesis 1b: At the 2-day retention test, effect sizes will support the same findings described for Hyp 1a.

Specific Aim 2: Establish evidence of increased spinal excitability following tsDCS.

Hypothesis 2: Spinal excitability post-stimulation (measured by H-reflex) will be significantly elevated above pre-stimulation baseline for active tsDCS but not sham tsDCS.

6. Research Plan:

Study Overview

All study procedures will be conducted at the Brain Rehabilitation Research Center within the Malcom Randall VA Medical Center. Up to forty older men and women will be enrolled in the intervention component of this study. A larger number will be enrolled for onsite screening, because some will fail the screening tests and not proceed to the study intervention.

Participants will undergo the following sequence of events:

- *Telephone Screening:* Volunteers will be screened by telephone to determine if they meet basic enrollment criteria including age and general health status.

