- Cognitive Assessment Battery from Cambridge Brain Sciences, which includes up to 12 cognitive tests. All are short, simple, computer-based assessment that assess domains of cognitive such as spatial working memory, response inhibition, and reasoning. A specific example is the visuospatial working memory test, in which participants are asked to remember the sequence and location of shapes that appear and disappear from the screen.

Following the screening visit, study staff will evaluate performance/responses relative to the study enrollment inclusion/exclusion criteria. Medical records may be examined to verify absence of exclusion diagnoses, and to obtain complete/accurate medication lists. Individuals who meet all criteria will be invited to enroll in the full study.

At the discretion of the Principal Investigator, any individual may be deemed ineligible for further participation in this study if there are concerns about the individual's capability to perform study procedures or if it may be unsafe for the volunteer to participate in the study. Furthermore, minor exceptions to the inclusion/exclusion criteria may be permitted at the discretion of the Principal Investigator if those exceptions do not influence participant safety. For example, small deviations from the target range of walking speed or somatosensory function. This is important to ensure that individuals are not excluded for insignificant reasons and to facilitate meeting enrollment benchmarks.

Walking Practice Visit(s)

Walking practice protocol

Walking practice will consist of 10-20 passes over a 10-meter complex walking course consisting of foam obstacles of various heights and widths, as well as transitioning between hard (bare floor) and soft surfaces (exercise mats). Each pass will be separated by a short rest period of approximately one minute. Participants will be instructed to walk as fast as safely possible.

For most participants, the walking practice protocol will be completed in a single visit. However, a subset of participants (up to 20) will perform the walking practice protocol twice so that we can study dosage effects (i.e., one session versus two sessions). This subset will be selected randomly.

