During the walking practice protocol, participants will receive either active or sham transcutaneous spinal direct current stimulation (tsDCS) and will wear either smooth or textures shoes insoles. Specifically, participants will be randomized to one of four groups: active tsDCS with smooth insoles (*active/smooth group*); 2) sham tsDCS with smooth insoles (*sham/smooth group*); 3) active tsDCS with textured insoles (*active/textured group*); and 4) sham tsDCS with textured insole (*sham/textured group*). More detail about tsDCS and insoles are given below.

Transcutaneous spinal direct current stimulation (tsDCS) during walking practice protocol
tsDCS will be delivered to the posterior lumbar region of the spinal cord during walking using a commercially available direct current stimulation unit (Soterix Medical Inc). Each tsDCS electrode is comprised of a carbon rubber electrode encased in a saline-soaked sponge. The anode electrode will be placed on the skin over the 11th and 12th thoracic vertebrae, and the cathode electrode will be placed over the umbilicus. This electrode configuration has been shown to appropriately target the lumbosacral spinal cord, as validated by modeling of electrical current flow⁴² and by gains in lower extremity motor performance.²⁵ A standard dosage of up to 30 continuous minutes of 2.5 mA stimulus will be used. This dosage (or similar) has been used in numerous prior studies and has been shown to be well-tolerated and to produce measurable changes in reflex activity and/or lower extremity motor performance.^{23-25,38,39,43,44} An identical electrode arrangement will be used for the sham condition, except the stimulation will be delivered in a brief ramp-like manner for just a few seconds at the beginning and end of the stimulation period. This sham approach is widely used in the field of direct current stimulation, and has been reported to be indistinguishable from active stimulation.^{39,45} This is because participants quickly habituate to the sensation of active stimulation.

Textured Shoe Insoles during walking practice protocol

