
fNIRS Safety: fNIRS poses no safety risk. Infrared light from the fNIRS device is not harmful and elicits no sensation. Sensors may be secured to the skin using adhesive tape, which could lead to mild skin irritation in those who are sensitive to adhesives. If a person indicates or displays such a sensitivity, we will avoid using adhesive tape and instead use elastic fabric or straps to secure the sensors.

Questionnaire administration: Questionnaire data are collected in secure spaces where the interview cannot be overheard. Participants will be informed that they are not required to answer questions that they do not wish to answer.

Statistical Analysis Plan: Effect sizes for between-group differences will be calculated for *improved* walking speed after the practice period. For Hypothesis 1b, an analogous comparison

will be made for the 2-day retention test. We do not claim that this study is powered to conduct statistically significant tests of group differences, although we will examine our data for evidence of directional effects:

[active/textured] > [active/smooth = sham/textured] > [sham/smooth].

Rather, our goal is to calculate effect sizes and variance of response in order to provide data needed for powering a future full scale trial. This study will also provide information on the feasibility of our protocol including safety and recruitment.

1. Fielding, R.A., W.J. Rejeski, S. Blair, T. Church, M.A. Espeland, T.M. Gill, J.M. Guralnik, F.C. Hsu, J. Katula, A.C. King, S.B. Kritchevsky, M.M. McDermott, M.E. Miller, S. Nayfield, A.B. Newman, J.D. Williamson, D. Bonds, S. Romashkan, E. Hadley, M. Pahor, and L.R. Group, *The Lifestyle Interventions and Independence for Elders Study: design and methods*. Journals of Gerontology. Series A, Biological Sciences and Medical Sciences, 2011. **66**(11): p. 1226-37.
2. Shumway-Cook, A., A. Patla, A. Stewart, L. Ferrucci, M.A. Ciol, and J.M. Guralnik, *Environmental components of mobility disability in community-living older persons*. J Am Geriatr Soc, 2003. **51**(3): p. 393-8.
3. Shumway-Cook, A., A.E. Patla, A. Stewart, L. Ferrucci, M.A. Ciol, and J.M. Guralnik, *Environmental demands associated with community mobility in older adults with and without mobility disabilities*. Phys Ther, 2002. **82**(7): p. 670-81.

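### The planned effect sizes for gain in walking speed have no covariate adjustment and ignore the randomised one- or two-session assignment, leaving avoidable variance in figures meant to power the next trial

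*Combined protocol and SAP*

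**What the plan says.** The Statistical Analysis Plan is one short section. It states that "Effect sizes for between-group differences will be calculated for" *improved* walking speed after the practice period, with an analogous comparison at the 2-day retention test. It disclaims power for group tests and gives its purpose as "our goal is to calculate effect sizes and variance of response in order to provide data needed for powering a future full scale trial". Section 5 (Specific Aims) words Hypothesis 1a the same way: "Within-session, effect sizes will support the following group differences for improved walking speed". Neither section names a covariate, a model, the passes that form the baseline, a standardiser or a confidence interval.

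Section 6 describes a second random assignment. The Study Overview says "They will attend either one or two intervention sessions (randomly determined to study dosage effects". The walking practice protocol says "For most participants, the walking practice protocol will be completed in a single visit", but that "a subset of participants (up to 20) will perform the walking practice protocol twice so that we can study dosage effects", and adds "This subset will be selected randomly". A repeated session also repeats the interventions: "During the walking practice protocol, participants will receive either active or sham transcutaneous spinal direct current stimulation (tsDCS", and they wear the assigned insoles. The Statistical Analysis Plan does not mention session number.

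The Study Overview and the Follow Up Visit section both time the retention test from the intervention visit, in the singular. For someone with two such visits, neither says which one counts.

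**The concern.** The effect sizes and the variance of response are what this pilot is meant to deliver, so how they are estimated matters even though no test is planned.

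- **Baseline.** An unadjusted change score is usually less precise than a comparison adjusted for the same baseline.
- **Session number.** A randomised factor that may affect retention is left in the error term. Its chance imbalance between arms goes uncorrected, and the dosage question that prompted it has no analysis.
- **Mixed dose.** The pooled 1b effect averages over one and two sessions, and the plan does not say so.
- **Standardiser.** An effect size reported without its standardiser can be misread when the next trial is sized.

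**Working it through.** **Plan's own figure.** There is none to reproduce. The documents give no SD, pre-post correlation, alpha, power or target effect, and 40 is not derived from anything.

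**Inputs.** From the documents: up to 40 participants, four groups, up to 20 with two sessions, and random selection with no stratification by group stated. Assumed: 10 per arm; equal pre and post SDs; correlation r = 0.5, 0.7 or 0.9; m = 5, 10 or 20 two-session participants; and a second session adding d = 0, 0.5 or 1.0 SD of change, equally in all arms unless stated.

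**Step 1, baseline adjustment.** With SD = 1, the change-score variance is 2(1 - r) and the ANCOVA residual variance is 1 - r². Their ratio is (1 + r)/2. Estimating one slope multiplies it by 1 + 1/34.
- r = 0.5: 0.75 × 1.0294 = 0.772
- r = 0.7: 0.85 × 1.0294 = 0.875
- r = 0.9: 0.95 × 1.0294 = 0.978

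**Step 2, ignoring session in 1b.** Within-arm variance is multiplied by 1 + p(1 - p)d², with p = m/40.
- d = 0.5: 1.027, 1.047, 1.063 for m = 5, 10, 20
- d = 1.0: 1.109, 1.188, 1.250

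With an unstratified draw, two given arms differ by three or more two-session participants with probability 0.09, 0.20 and 0.27 (simulated). At d = 0.5, a difference of three shifts that contrast by 3/10 × 0.5 = 0.15 SD.

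**Step 3, both adjustments together.** The variance relative to a raw change score that ignores session is (1 - r²) × 1.061 / [2(1 - r)(1 + d²m(40 - m)/1560)]. The factor 1.061 is the cost of two extra terms, averaged over random designs.

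| m | d | r = 0.5 | r = 0.7 | r = 0.9 |
|---|---|---|---|---|
| 5 | 0 | 0.795 | 0.901 | 1.007 |
| 5 | 0.5 | 0.774 | 0.877 | 0.980 |
| 5 | 1.0 | 0.715 | 0.810 | 0.906 |
| 10 | 0 | 0.795 | 0.901 | 1.008 |
| 10 | 0.5 | 0.759 | 0.860 | 0.961 |
| 10 | 1.0 | 0.667 | 0.756 | 0.845 |
| 20 | 0 | 0.796 | 0.902 | 1.008 |
| 20 | 0.5 | 0.748 | 0.848 | 0.947 |
| 20 | 1.0 | 0.633 | 0.718 | 0.802 |

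**Step 4, mixed dose.** If a second session changed an arm contrast by 0.5 SD, the pooled 1b contrast would shift by p × 0.5: 0.125 SD at 10 of 40 and 0.25 SD at 20 of 40. An additive session factor does not remove this (simulated 0.124 and 0.251).

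**Step 5, standardiser.** Change SD divided by baseline SD is √(2(1 - r)): 1.00, 0.775 and 0.447 at r = 0.5, 0.7 and 0.9. The same difference in m/s is therefore 1.00, 1.29 and 2.24 times as large on the change SD. If that effect were read as one on the baseline SD, the next trial would be too small by a factor of 1/(2(1 - r)) = 1.00, 1.67 and 5.00. At r = 0.3 the factor is 1/1.4 = 0.71, and the next trial would be too large.

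**Step 6, if there is no pre-stimulation course speed.** Suppose the gain were replaced by final speed adjusted only for screening 10 m speed, with assumed correlation s to final speed. Relative to the early-to-late change score, the variance is (1 - s²) × 1.0294 / [2(1 - r)].
- s = 0.5: 0.77, 1.29, 3.86 at r = 0.5, 0.7, 0.9
- s = 0.3: 0.94, 1.56, 4.68

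**The case against.** The strongest reply is that this is a pilot that disclaims power, and that the gains are small beside its own imprecision. A pooled SD on 36 degrees of freedom has a 95% interval of 0.81 to 1.30 times the estimate. That stands as a limit on the size of the point. It does not remove it, because the plan makes these estimates its goal and the adjustment is nearly free.

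Four stronger readings are tempting, and the documents do not support them.
- **That baseline is ignored.** A gain score already subtracts it. What is missing is covariate adjustment and a definition of the baseline passes.
- **That the session mix biases the arm comparison.** The subset is chosen at random, so the consequences are variance, chance imbalance and an averaged dose.
- **That the next trial would be five times too small.** This needs r = 0.9 and a later planner who misreads the standardiser, and the error reverses below r = 0.5. The promised variance of response may also include the change SD, which would make the misreading less likely.
- **That session number affects every result.** Hypothesis 1a is within-session. If the first session is used for everyone, only 1b is affected. Dosage appears in no specific aim.

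Two practical objections also stand. The documents describe no obstacle-course pass before stimulation, so the preferred covariate may not exist; Step 6 shows that dropping the gain in favour of screening speed can then do harm. By-arm results within the two-session subset would often not be estimable: at least one arm has no two-session participant with probability 0.73 at 5 of 40 and 0.14 at 10 of 40.

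**Conclusion.** The point holds as a modest and inexpensive improvement in efficiency and reporting. The plan adjusts for no covariate and leaves a randomised factor unused. Over the assumed range, baseline adjustment alone brings the variance of an arm difference to 0.772-0.978 of the raw change score's. Ignoring session inflates within-arm variance in 1b by about 3-6% at 0.5 SD and 11-25% at 1.0 SD. The top of each range uses 20 of 40, which is the stated upper limit; the statement that most participants complete practice in one visit points to fewer. There is no gain at r = 0.9 with no session effect.

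All correlations, session effects and the 10-per-arm split are assumptions. That the plan omits the adjustment and any use of session number is plain from the text.

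**What to change.** - **Model.** Estimate arm differences in 1a (first session for everyone) and 1b by a four-arm ANCOVA with pre-stimulation obstacle-course speed as covariate. Add randomised session number as a factor in 1b. Say which passes are baseline and which are end of practice, and which visit the retention test follows for two-session participants.
- **If no pre-stimulation course speed exists.** Keep the planned gain score as the outcome and add screening 10 m speed only as an extra covariate. Do not replace the gain with final speed adjusted for screening speed alone: that drops the practice-related gain of Aim 1 and can raise the variance.
- **Dose.** State that the 1b estimate averages over one and two sessions, and that the additive factor does not remove an arm-by-session interaction. Show the one- versus two-session difference overall. Give by-arm results descriptively, and only where arms contain two-session participants.
- **Reporting.** Give the adjusted difference in m/s with a 95% CI, the standardised effect with its standardiser named, and the SD of change. Where a course baseline exists, add the baseline SD, residual SD and pre-post correlation, so that effect sizes are not misread in either direction.

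The cost is plan wording and a little analysis, with no new visits or measurements. It uses one degree of freedom in 1a and two in 1b. With a course baseline, the worst case over the range shown is about a 1% variance loss, at r = 0.9 with no session effect.
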